Validation of a record-based frailty assessment according to the Multidimensional Prognostic Index

[name]
Aarhus University Hospital
January 30th, 2019

Validation of a record-based frailty assessment according to the Multidimensional Prognostic Index

Background

Various phenotype and cumulative frailty assessment tools have been developed and compared in research (1). For use in an in-hospital setting, a cumulative and graded frailty assessment method is preferred in order to identify subgroups of patients at risk of adverse events during discharge and transition to primary care. Comprehensive Geriatric Assessment (CGA) is the gold standard to assess frailty (2). Most medical wards have limited access to specialized geriatric team support capable of performing CGA. Thus in these wards there is a need for a CGA based instrument to identify the frail patients and to quantify the level of frailty. The Multidimensional Prognostic Index (MPI) (3,4) is based on CGA and is a comprehensive cumulative deficit frailty assessment tool validated in a Danish geriatric department (5). MPI is fully applicable in the everyday clinical work and supplies useful information to clinicians. It can predict readmission and death (5), and it is well-suited to assess the degree of frailty (1,6). Enabling identification of patients at risk of adverse events facilitates targeting of the interventions in order to improve patient outcomes. The MPI is a bedside assessment. However, in observational record-based research the patient is not accessible for the researcher. To assess and identify hospitalized frail patients retrospectively for clinical research, a valid record-based frailty assessment method is needed.

Objectives

The aim of this study is to compare the accuracy of a record-based MPI assessment with a bedside performed MPI assessment in order to use the record-based MPI when access to bedside MPI is impossible.

Hypothesis

There is a high correlation ($\geq 70\%$) between the bedside MPI sum score and the record-based MPI sum score in 75+ year older hospitalized patients.

Materials and methods

This validation study is performed in a paired design with comparison of the bedside MPI compared to a record-based MPI of the same hospitalized patient at the same day.

Source of data

Bedside MPI:

The MPI screening tool for bedside use has been modified and validated as described by Gregersen et al. (5). The original MPI tool (3) consists of a combined score of eight items: co-habitation status, number of drugs used, activities of daily living (ADL) and instrumental activities of daily living (I-ADL), cognitive status, risk of pressure sores, morbidity and nutritional risk. In this study, the bedside MPI will be calculated using the following eight items: co-habitation status, number of drugs used, ADL and I-ADL by Functional Recovery Score (FRS), cognitive status by Short Portable Mental Status Questionnaire (SPMSQ), risk of pressure sores by Exton Smith Scale (ESS), morbidity by Cumulative Illness Rating Scale Geriatrics (CIRS-G), and nutritional risk by the Mini Nutritional Assessment Short Form (MNA-SF). All items except the CIRS-G will be assessed by a Research Assistant.

Record-based MPI:

The Danish civil registration register, the hospital medical record used in Central Denmark Region, and the community nurse medical chart are all linked in the Columna Clinical information system (Systematic) used in all hospitals in Central Denmark Region. Information on all eight MPI items needed to calculate the sum score with the exception of SPMSQ and BMI in the MNA-SF can be assessed through the clinical information system and without direct bedside access to the patient. The record-based MPI screening tool has been customized to these minor limitations (See Appendix A: Record-based MPI sum score and frailty level).

Fifty unique patients are needed in this validation study. They will all be assessed by both a record-based MPI performed by two independent raters (a Research Assistant and a PhD student), and by bedside MPI performed by a skilled physiotherapist or occupational therapist (see Fig. 1: Record-based and bedside MPI-screening). All raters will be blinded to the screening results. Enrollment to the MPI screening is performed during daytime on weekdays by the Research Assistant. The CIRS-G used in both methods will be calculated by the Research Assistant prior to the record based MPI-screening. The record-based MPI screening will be performed before the bedside MPI screening, using only the medical record information accessible at the time of screening

as described in Appendix A. The inclusion takes place from December 4th, 2018 until the total of 50 patients has been reached. The inclusion will be paused during weekends and holidays.

Patients

The study group comprises medical patients acutely admitted to the Department of Cardiology (DC), and the Department of Infectious Diseases (DID), Aarhus University Hospital (AUH). Participants can only be included once.

- **Inclusion criteria:**
 - Aged 75 years or older
 - Living within the municipality of Aarhus
- **Exclusion criteria:**
 - Included in any other kind of follow-up schemes
 - Already included in this study
 - Declared terminally ill or undergoing palliative care at admission
 - Admitted from one specific temporary nursing home with geriatric medical assistance (Vikærgården)
 - Discharge or transfer to another department, including hospice
 - The patient does not want to participate in the MPI-screening process

Statistical analysis

Reasonable precision for estimates of reliability requires at least 50 study participants (7). The bedside MPI serves as a gold standard and will be held up against the record-based MPI. The relative difference between the two measurements' sumscores is calculated as an Intraclass Correlation Coefficient (ICC). It is recommended that the ICC exceeds 70% in order to be regarded as acceptable (8). This method is controlled by calculating the correlation between the difference and the average by using the Pearson's statistics. Assumption of independence is examined in a Bland-Altman plot and normal distribution of the differences will be checked in a QQ plot. Limits of agreement are prediction intervals for the difference and will be presented in a figure. The within-subject random variation (standard error of measurement) and the systematic change of the mean will be calculated. Also, the inter-rater reliability of two raters using the record-based MPI will be examined in the same way. We will examine how consistent the results are for the each of the eight different items and for the construct within the measures. The internal consistency is analyzed by Cronbach's Alpha. Researchers have proposed that the minimum item-total correlation should be 0.20 (9). Data are registered in REDCap and exported to STATA version 15 for the statistical calculations.

Perspectives

This study may prove that retrospective, record-based MPI frailty assessment is a valid way to assess frailty for scientific use, compared to bedside performed MPI, thereby enabling retrospective inclusion of control group patients in larger scale studies.

Ethics

The study has been approved as a quality development project by the Regional Research Ethics Committee, Central Denmark Region (journal no. 197/2017), thereby no patient consent form is needed, and further referral to the committee not required. No patient will receive less than usual care, no extra treatment or examination will be applied, and no patient will be exposed to any additional risk because of the study. Participants may decline participation at any point. The project, which is a part of the national rate adjustment pool-project "Early post-discharge follow-up of the frail elderly – a intersectoral effort" in the Central Denmark Region, is approved by the Danish Data Protection Agency (journal no. 2012-58-006).

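### One CIRS-G score feeds both the bedside and the record-based MPI, and no sum-score analysis leaves it out; the ICC held against 70% may be slightly raised, by an amount the documents do not fix

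*Combined protocol and SAP*

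**What the plan says.** Under Materials and methods (Record-based MPI) the plan says: "The CIRS-G used in both methods will be calculated by the Research Assistant prior to the record based MPI-screening". The Research Assistant is also one of the two record raters, since each patient is to have "a record-based MPI performed by two independent raters (a Research Assistant and a PhD student").

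The conversion table in Appendix A gives CIRS-G one of eight equally weighted places, scored 0, 0.5 or 1, and divides the total by 8. Only the record-based table is given.

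The Hypothesis concerns the correlation "between the bedside MPI sum score and the record-based MPI sum score". The Statistical analysis section computes the ICC, standard error of measurement (SEM) and limits of agreement on the sum scores and sets the criterion: "It is recommended that the ICC exceeds 70% in order to be regarded as acceptable (8"). It plans item-by-item consistency for all eight items and the same analysis for the two record raters. It describes no sum score without CIRS-G.

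On who rates the bedside items, the Bedside MPI paragraph says "All items except the CIRS-G will be assessed by a Research Assistant". The Record-based MPI paragraph says patients are assessed "by bedside MPI performed by a skilled physiotherapist or occupational therapist" and gives CIRS-G to the Research Assistant.

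**The concern.** An agreement study asks how far two measurements differ when each is made in its own way. An item that is scored once and copied into both sums contributes between-patient variance but no disagreement. That tends to push the ICC up and to narrow the SEM and the limits of agreement, in the direction that favours meeting the 70% criterion. A confidence interval would not show the shift, because it is not sampling error.

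The planned item-level results would show identical CIRS-G scores but would leave the sum-score ICC unchanged. For any pair of ratings that shares the score, item agreement on CIRS-G carries no information.

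The same question arises for inter-rater reliability. The plan calls the record raters independent, yet describes one CIRS-G calculation, made by one of them before the record screening.

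**Working it through.** **Plan's own figure.** The 50 patients come from a cited rule. No expected ICC, interval width or power is given, so there is nothing to reproduce. For context, with 50 patients and two ratings, an observed ICC of 0.70 means F = 1.70/0.30 = 5.667. Dividing and multiplying by the 97.5% F quantile with 49 and 49 degrees of freedom (1.762) gives 3.216 and 9.985. With ICC = (F − 1)/(F + 1), the 95% CI is 0.53 to 0.82.

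**Formula.** Write the ICC as covariance of the two sums over variance of the sum. Copying CIRS-G replaces the covariance of two separate scorings, a × Var(CIRS-G), by Var(CIRS-G), where a is the agreement of two separate scorings of the 0/0.5/1 item. With exchangeable methods and unrelated errors nothing else changes, so

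rise = (1 − a) × Var(CIRS-G) / Var(sum).

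It is zero if CIRS-G is constant or if a = 1.

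**Inputs.** Eight equally weighted items: Appendix A. Everything else (CIRS-G distribution, item variances, inter-item correlation r, agreement a, bedside bands equal to the record-based ones) is assumed, because the documents do not give it.

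**Equal item variances.** Var(sum) = 8(1 + 7r) item variances, so rise = (1 − a)/[8(1 + 7r)].
- r = 0: 0.1/8 = 0.012 at a = 0.9; 0.5/8 = 0.062 at a = 0.5.
- r = 0.2: 0.1/19.2 = 0.005; 0.5/19.2 = 0.026.

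**Unequal variances.**
- CIRS-G variance a quarter of the others', as when most patients fall in one category: 0.001 (r = 0.3, a = 0.9) to 0.017 (r = 0, a = 0.5).
- Twice the others', r = 0, a = 0.5: 0.5 × 2/9 = 0.11. Values above 0.10 need this kind of excess variance or almost no agreement between separate scorings.

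**Simulation.** Three-level items were cut from correlated normal variables and analysed with an absolute-agreement, single-rating ICC (the plan does not name the form). Over a broad grid the rise reached about 0.07. Two examples near the threshold, as seven items / eight scored independently / eight with CIRS-G copied:
- CIRS-G in thirds: 0.629 / 0.680 / 0.702, a rise of 0.022. SEM and limits narrow by 1 − √(0.298/0.320) = 3.5%.
- 84% in the top category: 0.677 / 0.695 / 0.703, a rise of 0.008. SEM and limits narrow by 1 − √(0.297/0.305) = 1.3%.

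Both examples set the reliability of the underlying continuous CIRS-G variable at 0.8. After cutting into three levels, the agreement of the scored item is only about 0.69 and 0.60. Rescaled to a scored-item agreement of 0.8:
- Thirds: 0.022 × 0.20/0.31 = 0.014.
- 84%: 0.008 × 0.20/0.40 = 0.004.

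**Effect on the decision.** P(observed ICC ≥ 0.70) is the upper tail of F(49,49) at 5.667 divided by (1 + ICC)/(1 − ICC).
- 0.680: 5.667/5.25 = 1.079, giving about 40%. 0.702: 5.667/5.711 = 0.992, giving 51%.
- 0.695: 47%. 0.703: 52%.

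These belong to the larger rises of 0.022 and 0.008, placed next to the threshold on purpose.

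**Related errors** (same latent reliability of 0.8; thirds, then 84%). At an error correlation of +0.1 the rise is 0.038 and 0.016; at −0.1 it is 0.002 and 0.000; at −0.2 the ICC falls by 0.014 and 0.007. The direction is therefore conditional.

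**What a seven-item ICC shows.** In both examples above it lies further from the independently scored eight-item ICC than the shared one does (0.051 against 0.022; 0.018 against 0.008). With r = 0 and an unreliable CIRS-G the three values were 0.689 / 0.655 / 0.728, so the seven-item figure can also lie above the independent one. It neither estimates nor bounds it.

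**The case against.** The best defence is that CIRS-G looks record-derived whichever method is used. The plan says that "Information on all eight MPI items needed to calculate the sum score with the exception of SPMSQ and BMI in the MNA-SF" is available from the clinical information system; Appendix A says CIRS-G can always be obtained; and the Bedside MPI paragraph sets it apart from the other items. On that reading, sharing one score removes rater error from a comparison of methods and hides no bedside-versus-record difference. That is a defensible choice, openly stated. This stands, and it is the better-supported reading. What remains is that rater error in CIRS-G is absent from the headline ICC, although the retrospective use foreseen under Perspectives would include it.

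Three further objections stand in part. First, agreement by construction assumes that the bedside score uses the same CIRS-G bands and weights, and the bedside table is not in the documents. Second, the effect is smaller than the sampling error. Third, the documents do not say which CIRS-G the PhD student uses. The single calculation before record screening and the single CIRS-G entry in the Fig. 1 text, whose layout is lost, suggest a shared score but do not establish it.

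A reader might also cap the rise at about 0.045 by keeping only settings that meet the item-total criterion: "Researchers have proposed that the minimum item-total correlation should be 0.20 (9"). The plan cites this as a proposed minimum, not as an expected property of these data, so it does not justify narrowing the range.

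**Conclusion.** The point holds in a limited form. One CIRS-G enters both scores, and no planned sum-score analysis leaves it out. Given matching bands and weights, between-patient variation, imperfect agreement between separate scorings, and errors that do not run opposite to those of the other items, the ICC is raised and the SEM and limits are narrowed. Under assumed inputs the rise is about 0 to 0.07, and about 0.014 or 0.004 at a scored-item agreement of 0.8. It can change the conclusion only near 0.70.

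A reader might infer that the shared item invalidates the comparison, or that the ICC is certainly inflated by a material amount. The documents support neither: they give no CIRS-G distribution or agreement, they point to a record-derived score in both methods, and the effect can be zero or reversed. Nor do they establish that the two record raters share the score. If they do, the inter-rater ICC is raised in the same way, and that is where independent scoring matters most.

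The two statements on who rates the bedside items conflict and need reconciling, but that is separate from any bias and adds nothing to its size. Severity: minor, a cheap improvement.

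**What to change.** 1. **Inter-rater analysis.** Have the PhD student score CIRS-G from the record, blinded to the Research Assistant's score, and use each rater's own score. If data collection is over and the score was shared, also report a seven-item inter-rater ICC.
2. **Bedside versus record.** Keep the eight-item ICC as the hypothesis test. Report the seven-item ICC beside it as a sensitivity analysis only, and say that it is not an estimate of, bound on or correction to the independently scored ICC. State that the eight-item result includes a shared item.
3. **Item-level results.** Leave CIRS-G out for any pair that shares it, and report its category frequencies so that readers can judge the likely size.
4. **Wording.** Reconcile the sentences on who rates the bedside items and CIRS-G, and state the source of CIRS-G for each of the three MPI scores.

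Cost: about 50 extra CIRS-G ratings by an existing rater from records already being read, one extra ICC per comparison that shares the item, and probably a slightly lower inter-rater ICC. No extra patients or staff. If enrolment is complete, only the re-analysis and the wording remain.

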APPENDIX A: Record-based MPI sum score and frailty level

The bedside-assessment of MPI frailty level has been validated and slightly modified, and is performed as described by Gregersen et al. (5). The record-based MPI is a little further revised, since some information is not directly achievable or even unachievable in the medical records. The record-based assessment is made using the medical record information obtained from the municipality nurses and home care staff at admission and information provided by physiotherapists, nurses, occupational therapists, home care staff, municipality nurses, social workers and doctors during admission. In case of divergent information, the most recent information is considered right. In case of lack of information on the separate items, values are estimated based on the overall impression after reading the medical record.

Co-habitation status: is always provided

Number of drugs: is always obtainable

FRS-ADL: some values are estimated based on the overall impression after reading the medical record. If no information at all is obtainable from the medical record, the patient is considered self-sufficient.

FRS-I-ADL: some values are estimated based on the overall impression after reading the medical record. If no information at all is obtainable from the medical record, the patient is considered self-sufficient.

SPMSQ: Since no testing can be performed, the SPMSQ is by default 3, unless the patient is described as delirious, confused or in other ways unable to answer the questions. If the patient has been diagnosed with any degree of dementia the score is 10 points.

ESS: if no information is obtainable, the patient is considered alert, mobilized and continent.

CIRS-G: is always obtainable

MNA-SF: is modified with regards to neuropsychological problems and with regards to Body Mass Index (BMI) as described below, since the information is often unavailable or indistinctly described in the medical record.

Modified SPMSQ:

Default (no testing possible)	3 points
Delirium, confusion or in other way unable to answer questions	5 points
Diagnosed dementia	10 points

Modified MNA-SF:

	Point
A Has food intake declined over the past three months due to loss of appetite, digestive problems, chewing or swallowing difficulties? 0 = Severe decrease in food intake 1 = Moderate decrease in food intake 2 = No decrease in food intake	
B Weight loss during the last 3 months? 0 = Weight loss greater than 3 kg (6.6 pounds) 1 = Does not know 2 = Weight loss between 1 and 3 kg (2.2 and 6.6 pounds) 3 = No weight loss	
C Mobility 0 = Bed or chair bound 1 = Able to get out of bed/chair, but does not go out 2 = Goes out	
D Psychological stress or acute disease	0 (all hospitalized patients)
E Neuropsychological problems: 0 = Severe dementia or depression (diagnosed dementia, mild or severe; or diagnosed with depression, moderate or severe; or treated with anti-depressants) 1 = Mild dementia (diagnosed with mild cognitive impairment or diagnosed dementia of mild stage; diagnosed mild depression (not treated with anti-depressants); described some degree of cognitive impairment, but undiagnosed 2 = No psychological problems	
F Estimated BMI 0 point if BMI <19, or if patient is described as underweight, cachectic, malnourished or as suffering from sarcopenia or atrophy of the muscles. 1 point if BMI between 19 and 21, or if state of	

nutrition is not described. 2 points if BMI between 21 and 23, or described as of normal weight or well nourished. 3 points if BMI above 23 or described as overweight or obese.	
Score: (max 14 points) 12-14 points: Normal nutritional status 8-11 points: At risk of malnutrition 0-7 points: Malnourished	

Record-based MPI sum score conversion table:

	low (=0)	moderate (=0,5)	severe (=1)
Co-habitation	With relative	institution	alone
Number of drugs	0-3	4-7	8 or more
FRS (ADL)	77-60	59-37	36-0
FRS (I-ADL) (modified)	19-13	12-9	8-0
SPMSQ	3	5	10
ESS	16-13	12-9	8-4
CIRS-G	0	1-2	3 or more
MNA-SF (modified)	12-14	8-11	0-7
SUBTOTAL	0	(0-4)	(0-8)
TOTAL	X	X	(0-8)
Record based MPI sum score = TOTAL divided by 8	X	X	(0-1)

Sum score to MPI frailty level conversion table:

Sum score	0,0-0,33	0,33 – 0,66	0,66 – 1,0
Frailty level	1	2	3

FIG. 1: Record-based and bedside MPI-screening

Department of Cardiology (DC), and the Department of Infectious Diseases (DID), Aarhus University Hospital (AUH)

All consecutively discharged, acutely admitted patients aged +75 years of age

Living within Aarhus Municipality

Receiving daily care, or

CCI ≥ 1

Daily list of patients

CIRS-G

Record-based MPI made by PhD student and by Research Assistant (both blinded)

Bedside MPI made by physiotherapist or occupational therapist (blinded to the above assessment)

Inclusion and frailty assessment continues until at total number of 50 patients has been reached.

References

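### Item E of the record-based MNA-SF scores diagnosed mild dementia as both 0 and 1, with no rule to decide between them, and names moderate dementia at neither level

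*Combined protocol and SAP*

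**What the plan says.** Appendix A defines the record-based instrument. Item E of its modified MNA-SF has three levels.

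- **Level 0** covers "Severe dementia or depression (diagnosed dementia, mild or severe", and also a patient "diagnosed with depression, moderate or severe; or treated with anti-depressants".
- **Level 1** is for mild dementia. It covers a patient "diagnosed with mild cognitive impairment or diagnosed dementia of mild stage", mild depression not treated with anti-depressants, and cognitive impairment without a diagnosis.
- **Level 2** is for patients with no psychological problems.

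Appendix A also has two general rules about the record: "In case of divergent information, the most recent information is considered right", and "In case of lack of information on the separate items, values are estimated based on the overall impression after reading the medical record". For the separate SPMSQ item it states: "If the patient has been diagnosed with any degree of dementia the score is 10 points".

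The Record-based MPI section plans a "record-based MPI performed by two independent raters". The Statistical analysis section adds: "Also, the inter-rater reliability of two raters using the record-based MPI will be examined in the same way". That section also plans to look at consistency for each of the eight MPI items.

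**The concern.** A patient whose record plainly states mild dementia satisfies level 0 and level 1 at once. Two raters who read the same record and apply the sheet faithfully can give different scores. In the inter-rater analysis that difference would be attributed to the raters or the record, although it comes from the sheet. The same choice enters the comparison with the bedside MPI and the MNA-SF results at item level.

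Moderate dementia is not named at all: in item E the word moderate is applied only to depression. The sheet is also meant to outlive this study, since the Perspectives section foresees its use for retrospective control groups in larger studies. An unresolved rule would be carried into that work.

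**Working it through.** **Does any other rule settle it?** No.

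- The divergent-information rule concerns conflicting entries in a record. Here the record is consistent and the sheet gives two scores.
- The missing-information rule concerns gaps. It can cover dementia of unstated stage, but only through the rater's overall impression.
- The rule on any degree of dementia belongs to the SPMSQ and is not extended to item E.

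Two repairs are plausible. Level 0 may have been meant to read moderate or severe, as the level labels and the depression wording suggest. Or it may have been meant to cover every diagnosed dementia, as the SPMSQ rule does. They give mild dementia different scores.

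**Who is affected?** Patients with diagnosed mild dementia and no other basis for level 0 (anti-depressants, or moderate or severe depression).

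**Effect on the MNA-SF domain.** Inputs from Appendix A: A 0–2, B 0–3, C 0–2, D fixed at 0, F 0–3. The domain is 0 for 12 or more points, 0.5 for 8–11 and 1 for 7 or fewer.

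- Patterns of A, B, C and F: 3 × 4 × 3 × 4 = 144.
- A+B+C+F is at most 10, so the total is at most 10 with E = 0 and 11 with E = 1. Only the 7/8 cut can be crossed, and only when A+B+C+F = 7.
- That occurs in 1, 3, 6 and 8 of 36 patterns for F = 0, 1, 2 and 3: 18 of 144 (12.5%).
- The domain is then 1 with E = 0 and 0.5 with E = 1. The MPI differs by 0.5/8 = 0.0625.

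**Effect on frailty level.** Any diagnosed dementia sets the SPMSQ domain to 1. With the other six domains totalling T, the MPI is (T + 1 + 0.5)/8 or (T + 1 + 1)/8.

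| T | MPI, E = 1 | MPI, E = 0 | Level | Patterns of 3⁶ = 729 |
|---|---|---|---|---|
| 1.0 | 0.3125 | 0.375 | 1 vs 2 | 21 |
| 3.5 | 0.625 | 0.6875 | 2 vs 3 | 126 |

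No other T changes the level. Both conditions hold in 18 × 147 = 2,646 of 144 × 729 = 104,976 patterns (2.5%). These are counts of patterns, not proportions of patients.

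**Effect on the ICC.** The protocol gives no dementia prevalence, MPI SD or expected ICC. Assume n = 2 to 10 affected patients of 50, raters always taking opposite readings (worst case), SD 0.12 to 0.20, and baseline ICC₀ 0.70 to 0.90.

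- Expected discordant domains m = n × 18/144 if patterns are equally likely: 0.25 to 1.25. If all have F = 3, m = n × 8/36: 0.44 to 2.22.
- ICC = s_b/(s_b + s_e′), where s_b = ICC₀ × SD² and s_e′ = (1 − ICC₀) × SD² + (m/50) × 0.0625²/2, with the direction of disagreement random.

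| m | SD | ICC₀ | Fall in ICC |
|---|---|---|---|
| 0.25 | 0.20 | 0.70 | 0.0002 |
| 2.22 | 0.12 | 0.90 | 0.0054 |
| 5 | 0.12 | 0.70 | 0.0094 |
| 5 | 0.12 | 0.90 | 0.0120 |

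Five discordant patients would require 5/0.125 = 40 affected patients (equal patterns) or 5/(8/36) = 22.5, so 23 (all F = 3).

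**Editorial point.** The item maxima sum to 2 + 3 + 2 + 0 + 2 + 3 = 12. The stated maximum of 14 and the 12–14 band cannot be reached as written, but every attainable score is still classified correctly.

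**The case against.** The contradiction is not in dispute. The case on the other side is that it hardly matters, and much of that case stands.

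- **The labels point one way.** Level 0 is labelled severe and level 1 mild, so raters guided by the labels would both score mild dementia as 1. Opposite readings every time are unlikely, and if both raters read it alike the inter-rater loss is zero. This stands as a comment on likelihood. But the text inside level 0 names mild dementia explicitly, and an agreed reading would still leave the bedside comparison dependent on an undocumented choice.
- **Moderate dementia is only a drafting gap.** Both plausible repairs put it at level 0 and no wording supports another score. This stands: the real source of disagreement is mild dementia.
- **The loss is far below sampling error.** With 50 patients and two ratings, an approximate 95% half-width for the ICC is 1.96 × (1 − ICC²)/7, about 0.14 at 0.70 and 0.05 at 0.90. A fall of up to 0.005 disappears within that. This stands for the sum score. At item level a discordant MNA-SF domain differs by 0.5 on a 0–1 scale, not by 0.0625.
- **Frailty-level agreement is not a planned analysis.** Correct. Those counts only describe how far the score could carry.
- **Reporting results twice is excessive.** Only if no record is affected, in which case there is nothing to re-score. Otherwise it concerns one item in a few records.

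**Conclusion.** The point holds. As written, item E gives two scores for diagnosed mild dementia, no rule in the protocol chooses between them, and moderate dementia is named at neither level. This follows from the text alone and needs no assumption.

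The size is small: one MNA-SF point in every affected patient, and 0.0625 on the MPI in those whose other variable items total 7. The expected fall in the inter-rater ICC is at most about 0.005 under the assumed ranges, and 0.012 in the stress case of five discordant patients. Those figures rest on assumed prevalence, SD and baseline ICC and on raters who always disagree. No conclusion about the 70% criterion is likely to turn on it. The reason to correct it is that the instrument under validation should not contain a rule that contradicts itself. It should be corrected, but it does not threaten the study.

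**What to change.** 1. Before record-based and bedside scores are compared, reconcile the two levels of item E so that diagnosed dementia of each stage (mild, moderate, unstated) falls at one level only. The choice is the sponsor's. Record the reason and give the rule to both record raters.
2. Have each rater independently re-score item E in affected records already assessed, using only the information available at the time of the first screening. Keep the original scores, because they are the reliability data for the sheet as used. Report the inter-rater and bedside comparisons with both sets. If no record is affected, say so.
3. As an editorial correction, state the attainable maximum as 12 in the score line and the conversion table, and confirm that bedside item D is scored in the same way.

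The cost is two or three lines in Appendix A, one item re-scored in any assessed records with diagnosed dementia, and a second set of agreement results. The number of such records is not given; inclusion began on 4 December 2018, 57 days before the protocol date of 30 January 2019. No new data are needed.
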